1 INTRODUCTION

1.1 BACKGROUND

Meshes are indicated to reinforce absent or weakened soft tissue. Their main clinical application is found in hernias and abdominal wall defects. [1-3] In these diagnoses, the fascia underlying the abdominal muscles (rectus abdominus, transverse, internal and external obliques) exhibits a defect. The fascia is a layer of dense organized connective tissue that resists tension forces. It is comprised of closely packed bundles of organized collagen fibers, produced by the resident fibroblasts. [4, 5]

A defect in the fascia allows abdominal contents, e.g. the viscera, to migrate or 'herniate' to a position outside the abdominal cavity, under the skin. Ventral hernias are common and are often the result of previous abdominal surgeries where the sutured fascia ultimately fails (incisional hernia). [6, 7] The term 'abdominal wall defect' is reserved for situations where a substantial section of the fascia is missing, and surgical repair is challenging. This can be caused by failed previous surgeries, infections, trauma and other causes. Many subjects with ventral hernias or abdominal wall defects suffer from co-morbid conditions that can have a negative impact on healing, such as obesity, diabetes, COPD, steroid use, or the presence of a stoma, [8] which may add to the complexity of the surgical repair and recovery. Reported recurrence rates after ventral hernia repair range from 2.7% to 62%. [2] [9-13]

The goal for surgical repair of these ventral hernias is to obtain a tension-free primary closure of the defect in [1-3] the fascia, although this is not always possible. Techniques used to create more 'real estate' to achieve this goal, such as component separation, result in an increased surface area, but an overall thinner, and thus potentially weaker, abdominal wall. [1, 14] To reinforce the abdominal wall, many hernia surgeries include the use of a mesh. In cases where primary closure has been achieved, the mesh is used to reinforce the fascia and is placed either on top or below the newly constructed abdominal wall. e.g. 'onlay' or 'underlay'.[15] In cases

where primary closure cannot be achieved meshes are used to bridge the remaining defect, e.g. 'inlay'.[16]

There exist two main classes of meshes, synthetics made of materials such as polyester, polypropylene, polytetrafluoroethylene (PTFE); and biologic ones that consist of decellularized extracellular matrix from different organs and species. Within these classes many different implants exist. [17, 18] Some synthetic meshes include a resorbable coating on one or both sides to prevent or reduce the incidence and severity of adhesions. The advantages of synthetic meshes are that they are strong, provide a permanent repair without developing laxity, can be designed in different shapes and are relatively low cost. [19] Disadvantages of synthetics include that they may need to be removed in the presence of infection, are prone to adhesions, promote scar formation instead of de novo fascia, become brittle over time, shrink, and can cause 'meshomas' or migrate and erode through organs. [20-22]

Biological meshes are made from connective tissue known as 'extracellular matrix'. These meshes are made from dermis, small intestine, bladder, pericardium and other organs rich in connective tissue. In the manufacturing process the extracellular matrix is separated from associated layers and decellularized via mechanical and chemical processes. The structure of the matrix is preserved as much as possible. The composition of the extracellular matrix is virtually identical among all mammals. Its main constituent is fibrillar type I and III collagen; it also contains adhesion molecules such as proteoglycans, glycosaminoglycans (GAGs), and other glycoproteins. These molecules play numerous structural and functional roles, including binding and presenting growth factors to cell surface receptors, interacting directly with cells via specific receptors including integrins, and forming complex extracellular structures. Many of these functions are crucial to remodeling the implanted matrix into functional native tissue. [23]

The collagenous matrix however is sensitive to damage caused by manufacturing processes, including terminal sterilization. The damage inflicted can take the form of fragmentation, cross-linking, or denaturation. The resulting matrix may no longer be completely natural and may be

perceived as a foreign body by the host, and cause inflammation or become encapsulated. Each manufacturer uses different source materials and proprietary protocols to decellularize and sterilize their product, leading to marked differences in their mechanical and biological performance. [24, 25]

The advantages of effective biologic meshes include that they recreate a natural fascia, allow the surgeon to treat local infections while leaving the implant in-situ, cause minimal or no adhesions to the viscera and other tissues, do not shrink and do not lead to long-term complications such as 'meshomas' or erosion of organs.

None of the biological meshes on the market today meet all the criteria of an ideal implant. [26] The degree to which they fall short of the mark varies; disadvantages that are mentioned frequently are the development of laxity ('bulging') over time, true recurrences and the costs of the implants. [27, 28]

1.2 RATIONALE FOR VENTRAL HERNIA STUDY

In today's surgical practice, synthetic meshes are typically indicated for patients with low to moderate risk of post-operative complications, with expectations that the mesh will become integrated into a fascia like layer. Biologic meshes, on the other hand, tend to be reserved for use in patients with a high risk of post-operative complications, with the expectation that the product will remodel into de-novo native fascia. [8] In reality, neither product fully succeeds in achieving either of these goals. Poor outcomes associated with use of both types of product have prompted the development of a unique new product category of Reinforced BioScaffolds (RBS). It is hypothesized that RBS have all the characteristics and benefits of a biologic, e.g. avoiding complications of fibrosis, bowel erosion and infection, while retaining the strength of a synthetic material and providing adequate reinforcement to a poor/damaged fascia and as such are not prone to bulging and form an improved alternative in the repair of ventral hernias.

OviTex® Permanent 1S reinforced bioscaffold consists of an extracellular matrix with a light internal polymer skeleton. The biologic component of OviTex® Permanent 1S reinforced bioscaffold is derived from ovine rumen and available in several thicknesses (strengths) and reinforced using a monofilament polypropylene thread. The processing has been optimized to ensure preservation of the natural characteristics of the matrix, after which the material is freeze dried. Layers are subsequently sewn together and sterilized. The sewing pattern yields a 6 x 6 mm square open pattern. OviTex Permanent 1S includes one outer layer with a reduced 25 x 25 mm pattern on one side to reduce the risk of adhesions when placed in contact with the viscera.

It is hypothesized that the use of OviTex® Permanent 1S reinforced bioscaffold in abdominal hernia repair (in comparable subjects) will result in less seroma formation, the same percentage or fewer infections and fewer surgical repair related secondary procedures such as fluid aspirations or wound debridement. In addition, the use of OviTex® Permanent 1S reinforced bioscaffold is expected to result in a similar or lower rate of true recurrent herniations as reported for comparable prospectively studied subjects in the literature treated with other implants. [30-33] Surgical procedure related outcomes tend to occur within the first three months after surgery, and the recurrence of a hernia may occur at any point in time after treatment. This study focuses on the surgical outcomes over the first 3 months and continues for a total of 24 months to capture the longer-term incidence of hernia recurrences.

1.3 PREVIOUS EXPERIENCE (PRE-CLINICAL AND CLINICAL)

OviTex® Permanent 1S reinforced bioscaffold has been (and is being) evaluated in several animal models. A rat study comparing a previous version of the OviTex reinforced bioscaffold to Surgisis, a porcine small intestine derived biologic, has been completed. A non-human primate study was performed and the results were compared to other mesh products used in ventral hernia repair, both synthetics and biologics studied in the same model. The results of the primate studies show OviTex® Permanent 1S reinforced bioscaffold to perform equivalent or superior to the most widely biologic and synthetic meshes used in this field with regards to inflammation,

kinetics of cell repopulation, absence of seroma formation and handling. The study reports are currently being prepared.

[figure not shown]
A study in rabbits evaluating the formation of adhesions was recently completed, initial results show that Ovitex Permanent 1S implants are less prone to adhesion formation than the positive control (Prolene).

A previous embodiment of the Reinforced BioScaffold also constructed from layers of ovine rumen and monofilament polypropylene has been implanted in 19 patients. Seventeen were treated for inguinal hernia and two for ventral hernia. To date, no adverse events or recurrences have been reported in these patients.

1.4 DEVICE DESCRIPTION AND INTENDED USE

OviTex® Permanent 1S reinforced bioscaffold is a six-layer construct of ovine derived extracellular matrix (ECM) and are assembled by stitching together multiple sheets of ECM with monofilament polypropylene. An example of an OviTex device is shown in Figure 1 below. The device is individually packaged and supplied sterile in various sizes up to 400 cm². The device is supplied freeze dried and sterile in a "ready to use" in a peel pouch, and requires up to 5 minutes of rehydration time prior to implantation.

Figure 1: Image of OviTex 1S Permanent RBS

OviTex® Permanent 1S reinforced bioscaffold is intended for use as a surgical mesh to reinforce and/or repair soft tissue where weakness exists. Indications for use include the repair of hernias and/or abdominal wall defects that require the use of reinforcing or bridging material to obtain the desired surgical outcome.

2 OBJECTIVES, HYPOTHESES, PRIMARY AND SECONDARY ENDPOINTS

2.1 OBJECTIVES

The study is designed to demonstrate that, in subjects with comparable characteristics, the use of OviTex® Permanent 1S reinforced bioscaffold in ventral hernias leads to the same or lower percentage of early post-operative complications and true hernia occurrences as compared to prospective reports in the literature for either synthetic or biological meshes.

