		APPENDIX 7: STATEMENT OF INVESTIGATOR	
		APPENDIX 8: SUB-INVESTIGATOR AGREEMENT	59

PROTOCOL SIGNATURE PAGE

The signature below constitutes the approval of this protocol entitled **A** prospective, single arm, multi-center study evaluating the short-term clinical outcomes of ventral hernias treated with OviTex® reinforced bioscaffold, and provides the necessary assurances that this trial will be conducted in compliance of all stipulations of the protocol, including all statements regarding confidentiality, and according to local legal and regulatory requirements, the Food and Drug Administration, International Conference on Harmonization Good Clinical Practice E6 (ICH-GCP), and applicable US regulatory requirements.

Investigator's Printed Name		
Investigator's Signature	Date	

STUDY SYNOPSIS

Title	A prospective, single arm, multi-center study evaluating the clinical
	outcomes of ventral hernias treated with OviTex® Permanent 1S
	reinforced bioscaffold.
Investigational Product	OviTex® Permanent 1S reinforced bioscaffold
Protocol Number	TB2016.01.01
Study Design	A prospective, single arm, multi-center study
Number of Study Sites	Up to 7
Number of Subjects	100
Study Population	Male and female subjects at least 18 years of age presenting with ventral hernia
Study Treatment	OviTex Permanent 1S reinforced bioscaffold in hernia repair
Study Objective	The study evaluates the post-operative complications and re-
	herniations following the use of OviTex® Permanent 1S reinforced
	bioscaffold in subjects with ventral hernias.
Study Endpoints	Primary endpoints:
	1. Incidence of early post-operative surgical site
	occurrences or wound related events (e.g ileus, deep or
	superficial wound infection, seroma, hematoma, wound
	dehiscence, skin necrosis, fistulae) noted at the hernia repair site
	and occurring within the first three months of the ventral hernia
	repair.
	2. Incidence of other early post-operative
	complications (e.g. ileus, bowel obstruction, fistula) occurring
	within the first three months of the ventral hernia repair.
	Secondary endpoints:

	 
	Incidence of late post-operative surgical site occurrences or wound related events (e.g. ileus, deep or superficial wound infection, seroma, hematoma, wound
	dehiscence, skin necrosis, fistulae, bulging) noted at the
	hernia repair site and occurring > 3 months after index
	surgery.
	2. Incidence of other late post-operative
	complications (e.g. ileus, bowel obstruction, fistula)

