2.3 STUDY DESIGN

This is a prospective, single arm, multi center, study evaluating the early post-operative clinical course and the true hernia recurrence rate of ventral hernias treated with the OviTex® Permanent 1S reinforced bioscaffold device. The study will be conducted at up to 7 sites and uses a prospective, observational design. Refer to Section 5 below for the Statistical Considerations of the study.

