2.3.1 Rationale for the OviTex® Permanent 1S reinforced bioscaffold study

The purpose of the OviTex® Permanent 1S reinforced bioscaffold Study is to provide prospective data on the early post- operative clinical course and the true hernia recurrence rates in the repair of ventral hernias. Data relating to subjects with similar baseline characteristics will be correlated and compared to (prospective) published data where applicable.

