7 STATISTICAL CONSIDERATIONS AND DATA MANAGEMENT

7.1 SAMPLE SIZE

A sample size of up to 100 subjects is planned for this study. This is a sample of convenience and is estimated to be sufficient to allow assessment of clinical performance in this patient population.

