7.2 STATISTICAL METHODS

Statistical methods will be carried out in accordance with the Statistical Analysis Plan (SAP) developed for this study.

The majority of data will be expressed as descriptive statistics. A p-value of less than or equal to 0.05 will be considered statistically significant. Any confidence bounds will show two-sided 95% confidence interval limits. Categorical variables will be summarized by number and percent. Continuous variables will be summarized by total number (N), mean, standard deviation, median, min and max. It is anticipated that the data will be evaluated using standard parametric and non-parametric procedures. Analyses of particular interest will be:

1. Correlation of rate of surgical site wound infection to SSI wound classification, number of previous repairs and pre-morbid conditions.

- 2. Correlation of surgical site occurrences or wound related events to re-herniation, BMI, number of previous abdominal.
- 3. Correlation of number of previous repairs with true hernia recurrence
- 4. Correlation of a visible bulge at hernia repair site with true hernia recurrence
- 5. Correlation of subject abdominal wall function and QoL with bulging at the hernia repair site and hernia recurrence rates.

The primary and secondary endpoints of this study will be also be compared to the clinical outcomes reported for other prospective studies in the literature. The results will be compared for the group as a whole, and, if the numbers will allow this, for subgroups of subjects exhibiting similar baseline characteristics, such as size of the hernia, co-morbid conditions, number of previous abdominal procedures etc.

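### Section 2.1 promises to demonstrate rates no higher than the literature, but the supplied text gives no comparator rate, margin or success rule to support that word

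*Combined protocol and SAP*

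**What the plan says.** Section 2.1 states the aim in confirmatory terms: the study is designed to demonstrate that, in comparable subjects, use of the device "leads to the same or lower percentage of early post-operative complications and true hernia occurrences as compared to prospective reports in the literature", for synthetic or biological meshes.

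Other sections describe the study more modestly:

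- Study Synopsis, objective: "The study evaluates the post-operative complications" and re-herniations.
- Section 2.3: the study "uses a prospective, observational design".
- Section 2.3.1: the purpose of the "Study is to provide prospective data on the early" clinical course and on recurrence.
- Section 7.1, on the number of subjects: "This is a sample of convenience and is estimated to be sufficient to allow assessment of clinical performance in this patient population".
- Section 7.2: "The majority of data will be expressed as descriptive statistics". It then adds: "A p-value of less than or equal to 0.05 will be considered statistically significant". No hypothesis or endpoint is attached to that level.

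The comparison with the literature is not confined to 2.1. Section 1.2 hypothesises less seroma, no more infections, fewer secondary procedures and a similar or lower recurrence rate. Section 2.3.1 plans a comparison with published data where it applies. Section 2.5 makes statistical comparison with the literature a reason for the interim analyses. Section 7.2 plans it for the primary and secondary endpoints, overall and in subgroups if numbers allow. Section 7.2 also refers to a separate SAP, which is not in the supplied text.

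**The concern.** To demonstrate a rate that is the same or lower, a single-arm study needs three things fixed beforehand: the rate to compare with, how far above it still counts as the same, and the result that counts as success. The supplied text gives none of them. A reader of 2.1 would expect a test with known error rates, while a reader of 7.1 and 7.2 would expect a description.

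What is at stake is what the sponsor may conclude. Section 7.3 plans outcome looks when the first 25, 50 and 75 subjects reach 90 days, and Section 2.5 allows enrolment to continue past 100 on the strength of interim analyses. Nothing supplied prevents the literature series, or the meaning of the same, from being settled after those looks.

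A smaller, separate problem lies in Section 1.2. It cites references 30 to 33 for comparable, prospectively studied subjects. By their titles in Section 10, references 30 and 31 concern inguinal hernia repair, whereas Section 2.7.1 enrols ventral hernias.

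**Working it through.** **Step 1: what a demonstration needs, against what is supplied**

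| Element | Supplied text |
|---|---|
| Comparator rate, early complications (primary endpoints, 2.2.1) | None |
| Comparator rate, recurrence (secondary endpoint, 2.2.2) | None designated; 1.1 gives only a background range |
| Rule for choosing literature series | Prospective, comparable subjects; no selection rule |
| Margin defining the same | None |
| Test or success rule | None; the 0.05 level in 7.2 is tied to no hypothesis |
| Null and alternative hypotheses | None in Section 2, although its heading promises hypotheses |
| Basis for N | Convenience (7.1) |

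The plan's figure of 100 has no stated inputs, so there is no calculation to reproduce.

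**Step 2: what 100 subjects could support, under assumed values**

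Input from the documents: n = 100 (7.1) and two-sided 95% limits (7.2). Assumptions of this review: benchmark p0 of 10%, 20% or 30%; margin m of 5, 10 or 15 percentage points; true rate equal to p0; benchmark known without error; all 100 subjects evaluable.

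Illustrative rule: same or lower is claimed if the upper exact (Clopper-Pearson) two-sided 95% limit lies below p0 + m. Let c be the largest event count that satisfies this. Then

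power = P(X ≤ c), with X ~ Binomial(100, p0).

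Worked case, p0 = 10% and m = 10 points (limit must be below 20%): 11 events give an upper limit of 18.8% and pass; 12 events give 20.02% and fail. So c = 11, and P(X ≤ 11 | 0.10) = 0.703.

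| Margin | p0 = 10% | p0 = 20% | p0 = 30% |
|---|---|---|---|
| 5 points | c = 7, 21% | c = 16, 19% | c = 25, 16% |
| 10 points | c = 11, 70% | c = 20, 56% | c = 30, 55% |
| 15 points | c = 16, 98% | c = 25, 91% | c = 34, 84% |

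The same sample runs from badly underpowered to well powered as the margin moves from 5 to 15 points.

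**Step 3: what an estimation objective would deliver at n = 100**

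Exact 95% intervals: 10 events, 4.9% to 17.6%; 20 events, 12.7% to 29.2%; 30 events, 21.2% to 40.0%. These need no benchmark or margin, and 7.2 already specifies two-sided 95% limits.

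**The case against.** The best defence is that benchmarks, margins and literature-selection rules normally belong in the SAP, which 7.2 names and which was not supplied. That stands: the gap is established for the supplied text only. The differing descriptions of the study in 2.1, the synopsis, 2.3 and 7.1 would still need aligning.

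It can also be said that this is a study of a commercially available product (8.3) with an openly declared convenience sample, and that no stopping decision is tied to 2.1. That limits the remedy to wording. It does not make the wording right, because the objective governs what may be concluded.

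Three stronger readings are tempting, and the documents do not support them.

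- *That 2.1 stands alone against a protocol planning no comparison.* Sections 1.2, 2.3.1, 2.5 and 7.2 all intend one. Evaluating outcomes and providing prospective data are also compatible with a comparative aim. What is missing is the framework.
- *That the conclusion could swing across the whole range in Section 1.1.* That section says "Reported recurrence rates after ventral hernia repair range from 2.7% to 62" percent. If the upper limit had to lie below the comparator, 51/100 recurrences (upper limit 61.1%) would pass against 62%, while 0/100 (3.6%) would fail against 2.7%. But the range is background, covers recurrence only, and is not shown to come from the comparable prospective mesh series that 2.1 requires. The rule is also one of superiority, whereas 2.1 asks for the same or lower: with a 5-point margin on 2.7%, the limit would be 7.7% and 0/100 would pass.
- *That 100 subjects are too few.* Step 2 shows that this depends on the margin.

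On the citations, only references 30 and 31 are a clear mismatch by title. The titles of 32 (contaminated hernias) and 33 (infected abdominal wall defects) leave comparability open, since wound Classes I to III are eligible and Appendix 2 places non-purulent inflammation in Class III.

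**Conclusion.** The point holds as one about the objective and its alignment, and should be fixed. Section 2.1 claims a property that the supplied design does not have. A literature comparison is intended throughout, but without a comparator rate, margin or success rule, and with no literature rate for the primary endpoints, the study as supplied can estimate and describe but cannot demonstrate.

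The size cannot be given as one number. In the illustration, power at 100 subjects runs from 16% to 98%, driven mainly by the margin. The benchmarks, margins and full follow-up are assumptions, so the figures show dependence on an unstated choice and do not show that the plan fails. Confidence is moderate, because the separate SAP was not seen.

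**What to change.** - **Section 2.1:** replace the objective with: The study is designed to estimate, with two-sided 95% confidence intervals, the rates of early post-operative complications and true hernia recurrence, and to present them beside rates from prospective literature.
- **Section 1.2:** mark all the hypotheses (seroma, infection, secondary procedures and recurrence) as background expectations that are not formally tested. Remove references 30 and 31 as comparable sources.
- **Section 2 heading:** drop the word Hypotheses.
- **Section 2.5:** change statistical comparison to descriptive comparison.
- **Section 7.2:** state that the literature comparison, overall and in subgroups, is descriptive and that the 0.05 level does not apply to it.

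If the SAP already fixes benchmarks and margins, cross-reference it in 2.1 and align these sections with it instead.

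The cost is text edits and a citation change; visits, data and sample size are unaffected. The downside is that the study can no longer claim to have demonstrated rates that are the same or lower.
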